12.3 Records Retention

Essential documents will be maintained for a minimum period of 7 years following completion of the study per UW-Madison institutional policy.

12.4 Retention for Future Research: Data and Audio- or Video-Recording Banking

12.4.1 Purpose of Storage

Essential documents will be maintained for a minimum period of 7 years following completion of the study per UW-Madison institutional policy. De-identified data will also be stored so that it can be made available to independent researchers wishing to verify our findings.

12.4.2 Data and/or Biospecimens Being Stored

Only de-identified data will be stored beyond completion of the study. De-identified data will include: a dataset comparing historical patients to those prospectively enrolled in the integrated care model and de-identified qualitative interview transcripts.

12.4.3 Location of Storage

De-identified data will be stored on the Health Innovation Program HIPAA compliant Server (P://), which is housed in a state-of-the-art data center at the Centennial Office Building managed by UW SMPH IT and is connected via fiber optic cable to the Health Innovation Program (HIP) suite at [name].

Data will also be stored on [name]'s UW Restricted ResearchDrive, the University of Wisconsin campus-wide file storage service managed by the Division of Information Technology. This is a secure space with data protection and security features based on the NIST Cybersecurity framework. It includes off-site backups, encryption, and monitoring by the University of Wisconsin Cybersecurity Operations Center.

12.4.4 Duration of Storage

Data will be retained for a minimum of 7 years per UW-Madison institutional policy.

12.4.5 Access to Data, Images, Recordings and/or Biospecimens and Security Measures

Access to identifiable data will be limited to those collecting it, so that they may check and confirm its accuracy, and those transcribing audio recordings of the qualitative interviews. The PI and research coordinators, and Drs. [name] and [name] (co-investigators) will work with de-identified data.

The following measures were put in place to protect confidentiality:

1. Access to identifiable data will be limited to those collecting data, conducting interviews, and transcribing interviews.
2. Data analysis, both quantitative and qualitative, will be performed on de-identified datasets and transcripts only.
3. The key linking de-identified study data to identifiable study participants will be kept by the research assistants generating this data on the HIPAA-compliant HIP server and [name] UW Restricted ResearchDrive.
4. Audio recordings of interviews will be destroyed after they have been transcribed and the transcripts were verified to be accurate by the person who conducted the interview. This limits accidental disclosure of identifiable information.
5. Original paper data abstraction forms will be kept in a locked filing cabinet in a locked office at the UW Medical Foundation Centennial Building. Using paper data abstraction forms limits cyber security issues.
6. Laptops will not be used for data collection, storage, or access.
7. Identifiable data will not be shared outside of UW.
8. Electronic data will be stored on the HIPAA-compliant HIP server, which has the following levels of security, and UW Restricted ResearchDrive:
 - a. Physical Security: the server is located in a secure data center under control of UW School of Medicine and Public Health (SMPH) IT, which is a dedicated computer machine room fitted with passkey access, video surveillance, emergency back-up power, an un-interruptible power supply, and an automatic fire detection and suppression system. SMPH IT does not have access to the server.
 - b. Firewall: the server is located behind the SMPH firewall.
 - c. Access Control: Data directory access is limited to HIP Faculty Director-approved individuals.
 - d. Domain Access Restrictions: access to HIP computing resources is restricted to individuals with a logon ID for the HIP Domain. Logon IDs are issued only upon approval of the HIP Director.
 - e. Authentication: Password protection is used at the network level for all transactions that allow entry and editing of data, provide access to electronic PHI data, or administrative activities.

12.4.6 Procedures to Release Data or Biospecimens

Authorized representatives of the following groups may need to review this research as part of their responsibilities to protect research subjects: authorized representatives of the sponsor, representatives of the IRB, DSMB/DMC, regulatory agencies, and federal oversight agencies. The clinical study site will permit access to such records following written request. The PI will also grant access to de-identified datasets upon reasonable request to independent researchers wishing to confirm our findings.

12.4.7 Process for Returning Results

N/A.

12.4.8 Process for Tracking Subject Consent and Authorization

Participants may withdraw consent by informing the PI in writing and specifying at that time whether they would like the study team to omit previously collected data pertaining to them from datasets and analysis. If this is not explicitly stated, the study team will use data collected about that study participant

from the time consent was originally signed up until the date the participant withdrew from the study. The research coordinator working with the clinic associated with the study participant who withdrew consent will be informed of their decision by the PI and asked to modify data sets and transcripts accordingly. It is the expectation that datasets will be amended due to participant withdrawal within one week of receiving written notice.

12.5 Protocol Deviations

A protocol deviation is any noncompliance with the clinical trial protocol or investigational plan requirements. The noncompliance may be either on the part of the participant, the investigator, or another member of the study team. As a result of deviations, corrective actions are to be developed by the study team and implemented promptly.

It is the responsibility of the Principal Investigator and all study team members to use continuous vigilance to identify and report deviations. The Principal Investigator is responsible for assessing whether the deviation constitutes noncompliance as defined by the reviewing IRB and if so, reporting it within the required time frames. The site investigator is responsible for knowing and adhering to the reviewing IRB requirements.

12.6 Publication and Data Sharing Policies

This study will be conducted in accordance with the following publication and data sharing policies and regulations:

National Institutes of Health (NIH) Public Access Policy, which ensures that the public has access to the published results of NIH-funded research. It requires scientists to submit final peer-reviewed journal manuscripts that arise from NIH funds to the digital archive PubMed Central (<https://www.ncbi.nlm.nih.gov/pmc/>) upon acceptance for publication.

This study will comply with the NIH Data Sharing Policy and Policy on the Dissemination of NIH-Funded Clinical Trial Information and the Clinical Trials Registration and Results Information Submission rule. As such, this trial will be registered at ClinicalTrials.gov, and resulting information from this trial will be submitted to ClinicalTrials.gov. In addition, every attempt will be made to publish results in peer-reviewed journals. Data from this study may be requested from other researchers up to seven years after the completion of the primary endpoint by contacting the PI in writing.

13.0 STUDY ANALYSIS

13.1 Statistical Hypotheses

- **Primary Efficacy Endpoint(s):**

- Completion of 5 vascular and 4 infectious disease care processes, modeled as percent indicated and dichotomously (all relevant completed vs. missing ≥ 1). *Hypothesis:* A larger proportion of patients in the integrated care model arm, compared to historical controls, will complete the 5 vascular and 4 infectious disease care processes.

- **Secondary Efficacy Endpoint(s):**

- Amputation, defined as either major or minor. *Hypothesis:* A smaller proportion of patients in the integrated care arm, compared to historical controls, will undergo either major or minor amputation within 3 months of diabetic foot ulcer diagnosis.

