Endpoints	
Primary Endpoints
 
 Completion of 5 vascular and 4 infectious disease care processes, modeled as percent indicated and dichotomously (all relevant completed vs. missing ≥ 1) Development and refinement of recruitment and retention strategies that meet our goal targets of 60% and 80%, respectively 
Secondary Endpoints
 
 Amputation, either major or minor, within 3 months of follow-up

[figure not shown]
Study Design	This is a phase II pre-post serial cohort design trial with adaptive recruitment and retention strategies. Enrollment will be implemented in two phases; healthcare systems will be enrolled in consecutive 6-month periods.
Study Intervention	A rural integrated care model consisting of a care algorithm for use by rural primary care providers to guide integrated care for patients with diabetic foot ulcers, and a referral checklist for use by rural schedulers to place referrals with urban specialists.
Total Number of Subjects	Up to 45 patient participants will be enrolled in the study with additional historical control patients obtained via chart review (1 active patient participant; 5 historical control patients, up to 180 patients total). Up to 30 healthcare workers will be enrolled (180+30=210 individuals participating in the care algorithm pilot). From the pool of patients and healthcare workers approached for recruitment, we will ask up to 36 individuals, consisting of 18 patient participants and 18 healthcare worker participants, to participate in feedback interviews; this group will be a mix of both those that enrolled in the integrated care intervention study and those that declined participation in the study. These individuals will provide qualitative data needed to build recruitment and retention strategies, meeting our second objective. We are uncertain of the exact mix of qualitative participants who will have consented or not to participate in the care algorithm pilot. Therefore, the total number of subjects is anticipated to be between 190 and 246, including historical controls.
Study Population	Patient participants are adults aged 18+ diagnosed with diabetic foot ulcers and receiving care at a participating clinic. Health workers include primary care providers, other healthcare providers such as specialists, and schedulers employed at a participating clinic.

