6.0 STUDY OBJECTIVES AND ENDPOINTS

Objectives	Endpoints
Primary	

Evaluate the potential of our integrated care model to reduce major amputations by examining its impact on guideline-concordant care processes, including urban specialty referral	A) Completion of 5 vascular and 4 infectious disease care processes, modeled as percent indicated and dichotomously (all relevant completed vs. missing ≥ 1) B) Amputation, either major or minor, within 3-month follow-up
Build recruitment and retention strategies for the trial that work across diverse, rural clinics	Development and refinement of recruitment and retention strategies that meet our goal targets of 60% and 80%, respectively

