10.2 Patient Participants

10.2.1 Study Calendar

The procedures performed at each study visit are listed in the table below.

Procedure	Screening	Baseline visit	Intervention	Telephone contact	End of Study/Early Withdrawal
Visit Window	Identification of Foot Ulcer	Next Clinic Visit		Month 3	
Telephone Screen	X				
Informed Consent		X			
Eligibility		X			
Integrated Care Model			X		
Chart Review		X	X	X	X
Follow-up				X	

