10.2.2.2 Informed Consent

Preliminarily eligible patient participants will be invited to participate in an informed consent discussion and formal screening at their next scheduled clinic visit. Potential patient participants are asked to come to the visit immediately after their scheduled clinic visit. The informed consent process will be conducted following all federal and institutional regulations relating to informed consent. The discussion will take place in a private room at the rural provider's clinic. Informed consent will be obtained prior to conducting any study-related activities. Immediately following signed informed consent, self-reported demographics will be collected using a standardized form to comply with NIH sponsor requirements.

The informed consent process will be performed as follows:

- A trained research coordinator will review the informed consent form and discuss the study in detail with the potential research participant.
- A trained research coordinator will explain the study, its risks and benefits, what would be required of the research participant, and alternatives to participation.
- The research participant will be given the opportunity to take the informed consent form home so that they may discuss it with family members, friends, clergy, or others when possible.
- The research participant will have the opportunity to ask questions and have all questions answered by the research coordinator.
- The informed consent document must be signed and dated by the research participant.
- A trained research coordinator will review the informed consent document to ensure that all fields that require a response are complete (i.e., checkbox marked yes or no, etc.) as applicable.
- The research participant will be given a copy of the informed consent form. The original signed and dated informed consent form is kept with the study records.

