10.2.2.3 Baseline Visit and Enrollment

Following informed consent, subject eligibility will be confirmed as follows:

A patient participant will be defined as "enrolled" in the study when they meet the following criteria:

- The patient participant has been consented by a research coordinator.
- The patient participant and a research coordinator have completed all screening documentation.
- The PI has verified that the patient participant meets all of the inclusion criteria.
- The PI has verified that patient participant meets none of the exclusion criteria.
- The patient participant completed a clinic visit with the participating rural provider, who considered recommendations outlined in the integrated care algorithm.

Following enrollment, the participant's medical record will be reviewed, and patient characteristic data will be abstracted. This will include sociodemographic data, comorbidities, medications, lab values, and ulcer characteristics. See Appendix for full list of variables.

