10.2.3 On-Study and Follow-up Procedures

10.2.3.1 Integrated Care Model Visit

Integrated Care Model activities will be performed by the rural provider and scheduler following the patient participants' enrollment in the study, as outlined above.

Following the rural provider visit, data on care processes will be abstracted from the participant's medical records. This includes information related to vascular disease care processes, infectious disease care processes, and other care processes. See Appendix for the full list of variables.

10.2.3.2 3 Month Follow-up

Patient participants will receive a follow-up call 3 months after their integrated care model visit (i.e., enrollment) to assess ulcer status and screen for any adverse events. This will be done by a research coordinator. Additionally, data will be abstracted from the patient's medical records. This includes medications, lab values, ulcer characteristics, and details of major or minor amputation, if applicable. If the patient participant is deceased at the time of the 3-month follow-up, information about the participant's death will also be obtained from medical records. See Appendix for the full list of variables. The following is a list of adverse events that will be tracked by the study team:

- Hypoglycemia requiring hospitalization or an emergency room visit
- Adverse reaction to a smoking cessation product
- Muscle aches after starting or changing a statin
- Complication of a revascularization procedure
- Adverse reaction to a wound care product or dressing
- Adverse reaction to an antibiotic prescribed for an infection complicating the diabetic foot ulcer
- Hospitalization for a diabetic foot ulcer (occurs in 30% of patients with diabetic foot ulcers)
- Major (above-ankle) amputation (risk increases with ulcer severity but is 5% in the overall national cohort of patients with diabetic foot ulcers)
- Death
- Patient reported adverse events that the patient attributes to study participation

All serious, unanticipated adverse events, deaths (whether anticipated or not), and major amputations (whether anticipated or not) will be reported to the ICTR DMC within 14 days of the study team becoming aware of these events.

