We received your contact information because [name of participating provider] is participating in our pilot study and you recently developed a diabetic foot ulcer. As an overview, the Crossing the Divide study was developed to improve treatment of diabetic foot ulcers for patients who live and receive healthcare in rural areas. This is a pilot study of an intervention to help clinicians provide care based on national standards. It was developed by clinicians and healthcare workers who practice in rural settings, with help from our research team. This current study will help us prepare for a larger study across rural Wisconsin, at which point we hope to find out how good the intervention is at getting people back on their feet.

To participate in the study, I will need to do a screening now over the phone to see if you qualify. If you do qualify and are interested in participating, you would come in 30 minutes prior to your next clinic visit to review and sign informed consent. At that time, you would receive \$100 for enrolling in the study. After that, participation includes just coming in for your regular visits with your doctor. We would also track your progress through your medical chart over the next 3 months. After that 3-month period, we would stop checking your medical record and give you a quick phone call to see whether your ulcer has healed. Once that phone call is done, you will have completed the study and receive another \$100 for your participation. In total, you would receive \$200 for enrolling in and completing the study.

Do you have any questions about the study at this time?

Would you be interested in completing the phone screening to see if you qualify for the study?

If no... Thank you for your time. Goodbye.

If yes, proceed.

As mentioned, if you choose to enroll and participate in the study, we would need to meet with you for 30 minutes prior to your next clinic visit. Before I can schedule that, I need to ask you a few questions while on the phone. The purpose of the questions are to determine eligibility for the study. This phone screening is voluntary, and you can stop the phone screening at any time. If you are not eligible for this study, we will record the reason as to why you are not eligible. The purpose of keeping this information is to allow us to track the number of people who have decided to enroll or not enroll in the study. Only our study personnel will have access to this information.

1. Call Attempt #1

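### Amputation is counted from ulcer diagnosis although active patients enter only at a later visit, and no section says which visit is a historical control's baseline for scoring the primary care processes

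*Combined protocol and SAP*

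**What the plan says.** **Amputation window.** Section 13.1 sets one origin for both arms: patients who "will undergo either major or minor amputation within 3 months of diabetic foot ulcer diagnosis". The Synopsis has "Amputation, either major or minor, within 3 months of follow-up" and section 6.0 has "Amputation, either major or minor, within 3-month follow-up"; neither says when follow-up starts.

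**Entry of active patients.** The study calendar (10.2.1) places screening at identification of the ulcer and the baseline visit at the "Next Clinic Visit". Section 10.2.2.3 makes enrollment conditional on several steps, the last being: "The patient participant completed a clinic visit with the participating rural provider, who considered recommendations outlined in the integrated care algorithm". The telephone script (Appendix 5, question 6) excludes anyone who does not report an ulcer or sore on the foot at the time of the call. Section 8.4.2 expects most patients to be identified soon after diagnosis but accepts that some will be found later.

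**Follow-up of active patients.** Section 10.2.3.2: "Patient participants will receive a follow-up call 3 months after their integrated care model visit (i.e., enrollment").

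**Controls.** Section 10.3.1 selects controls by working back in time from 3 months before clinic activation. Section 10.3.2 has their data abstracted at a baseline and 3 months after it. Neither section says which chart visit is the baseline.

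**Scoring.** Appendix 10 lists nine primary processes (5 vascular, 4 infectious disease). The pulse exam, smoking status and statin items refer to the baseline exam or visit, and a fourth item refers to baseline plain films. Date of diagnosis is among the abstracted variables.

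**The concern.** There are two problems with one cause: the plan has no common time zero for the two arms.

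The first concerns the secondary outcome. If the clock starts at diagnosis, an active patient must pass through the time to telephone screening with an ulcer still present, and then complete a clinic visit, before being counted at all. A patient whose ulcer was removed by an early amputation would not normally reach enrollment. A control with the same early amputation stays in the control group and counts as an event. Following 13.1 exactly therefore gives the active arm a stretch of largely protected time that the controls do not have.

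The second concerns the primary outcome. The natural default for a control is the first ulcer visit; the active baseline is the next visit after identification. Pulse checks, smoking and statin documentation and films may be done more or less often at a first ulcer visit than at a later one. Missing a single indicated item fails the dichotomous endpoint, so the choice of control visit could move the primary comparison for reasons unrelated to the care model.

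**Working it through.** **1. The plan's own figure.** Inputs from 13.2: 27 active patients, M = 5 controls each (135 controls, 162 in all), control probability p0 = 0.6, matched correlation 0.3, odds ratio ψ = 0.26, alpha 0.05 (taken as two-sided; the plan does not say). Stated power: 0.80706.

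Dupont's matched formula:
- p1 = 0.6 × 0.26 / (1 + 0.6 × (0.26 − 1)) = 0.156 / 0.556 = 0.281, and q1 = 1 − p1 = 0.719.
- The covariance term is 0.3 × √(0.281 × 0.719 × 0.6 × 0.4) = 0.066. The conditional control probabilities are a = 0.6 + 0.066/0.281 = 0.835 and b = 0.6 − 0.066/0.719 = 0.508.
- For k = 1 to M, t_k = p1·C(M,k−1)·a^(k−1)·(1−a)^(M−k+1) + q1·C(M,k)·b^k·(1−b)^(M−k).
- e_ψ = Σ k·t_k·ψ/(kψ+M−k+1), and v_ψ = Σ k·t_k·ψ·(M−k+1)/(kψ+M−k+1)².
- Power = Φ[(√27·|e_1 − e_ψ| − 1.96·√v_1)/√v_ψ].

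Results: 0.803 with M = 5, close to the stated 0.807, and 0.776 with M = 4 (27 × 4 = 108 controls). The definition of time zero does not enter this calculation; it matters only if controls are lost.

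**2. Order of events.**

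| Step | Active patient | Historical control |
|---|---|---|
| Ulcer diagnosed | amputation clock starts (13.1) | amputation clock starts (13.1) |
| Ulcer still present | required at telephone screening (Appendix 5) | not required |
| Completed later visit | required for enrollment (10.2.2.3) | not required |
| Baseline for scoring | next clinic visit (10.2.1) | not defined |

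The two middle rows create the non-comparable time on the diagnosis clock. The last row creates the scoring problem.

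**3. Possible size for amputation (illustration only).** The documents give neither the diagnosis-to-enrollment delay L nor a 3-month risk of any amputation. Assume a 91-day risk of 10%, no treatment effect, and active patients wholly amputation-free until enrollment. The last assumption overstates the case, since a minor amputation that leaves an ulcer is possible.

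Cumulative hazard H(t) = H91 × (t/91)^k, with H91 = −ln(0.90) = 0.1054. Active risk on the diagnosis clock = 1 − exp(−(H91 − H(L))). Example with k = 1 and L = 14: H(14) = 0.1054 × 14/91 = 0.0162, so the risk is 1 − exp(−0.0892) = 8.5%. The ratio to 10% is 0.85, and the shortfall in 27 patients is 27 × (0.10 − 0.0853) = 0.4 events.

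| Delay | Ratio, constant hazard (k = 1) | Events in 27 | Ratio, early-weighted hazard (k = 0.6) | Events in 27 |
|---|---|---|---|---|
| 7 days | 0.93 | 0.2 | 0.79 | 0.6 |
| 14 days | 0.85 | 0.4 | 0.69 | 0.9 |
| 28 days | 0.70 | 0.8 | 0.52 | 1.3 |

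If the Synopsis wording were read as 91 days from enrollment for active patients, with controls counted from diagnosis, the ratio would be 1.00 under a constant hazard and 0.84, 0.77 and 0.69 under k = 0.6. So the two readings can give different answers from the same charts.

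**4. Processes tied to baseline.** Vascular items 1, 2 and 3 (items 2 and 3 only partly, because counseling and statin start may follow within 3 months) and infectious disease item 1: 3 + 1 = 4 of 9. Nothing in the documents allows the effect of visit choice on these items to be sized.

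**The case against.** A reader might infer that 10.2.3.2 contradicts 13.1 by starting a second clock at enrollment. It does not. That section dates a telephone call and the chart abstraction made with it, not the amputation window. Appendix 10 has ulcer status, including amputation, assessed by chart review for all patients and records the date of diagnosis. Charts followed to 3 months after enrollment also cover 3 months after diagnosis, so the 13.1 outcome can be ascertained in both arms as written. The Synopsis and section 6.0 are less specific than 13.1 rather than in conflict with it. All of this stands. What remains is that an ascertainable outcome is still not a comparable one.

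A reader might also point to guaranteed survival to enrollment. Survival alone does not lower the active amputation count, and early control deaths would if anything remove chances for amputation, so no weight is put on it.

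The amputation effect is probably small. Identification is expected to be quick for most patients, and all but the most extreme row of the illustration shift by less than one event. Amputation is secondary in the Synopsis and 13.1, and the Synopsis says the study is not powered for major amputation. At the 5% national rate in 10.2.3.2 (no time window given), 0.05 × 27 = 1.35 major amputations would be expected. This limits the size of the point but does not remove it.

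On scoring, section 12.1.1 relies on standardized forms, which are not in the documents and might settle which visit is meant. The baseline films item could also mean the first film of a series. Neither supplies the missing definition in the plan itself.

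**Conclusion.** The point holds in two parts.

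First, the 13.1 rule gives active patients time from diagnosis to enrollment that is largely free of ulcer-removing amputation, while controls have no such protection. The direction probably favours the intervention. The size is unknown and likely small; the ratios above rest on an assumed 10% risk, assumed delays and an assumed hazard shape, and none of them is an estimate for this trial.

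Second, the control baseline is undefined although four of the nine primary processes are wholly or partly tied to it. If controls are scored at the first ulcer visit and active patients at the next one, the primary comparison mixes visit order with the intervention, in an unknown direction. A reader might infer that the primary result is biased by a material amount; the documents show the gap, not a bias of any given size.

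This should be fixed before the comparison is analysed. It does not affect the power calculation in 13.2.

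**What to change.** In 10.3 and 13.1:

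- Define one index visit that can be identified in the chart and apply it alike in both arms, with a current ulcer at that visit. The control visit that corresponds to the active baseline visit is the obvious candidate.
- Count amputation for 3 months from the index visit in both arms, and align the Synopsis and section 6.0 with that wording.
- Score the baseline items by one common rule, for example that any record from diagnosis through the index visit counts in both arms. Such a rule also makes the score less sensitive to the exact choice of visit.
- Report the diagnosis-to-enrollment delay in active patients, so that readers can judge how much the choice of origin matters. Date of diagnosis is already abstracted.

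No extra matching factor is needed. The cost is wording changes and some re-abstraction of control charts. A few controls may have no qualifying visit, and controls are already scarce: the amendment history says the options within the former date limit were exhausted. If controls are lost, restate the power, which recomputes to about 0.80 with 5 controls per active patient and 0.78 with 4.
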